#### • A congenital anomaly/birth defect.

Important medical events that may not result in death, are life-threatening, or require hospitalization may be considered serious when, based upon appropriate medical judgment, they may jeopardize the subject and may require medical or surgical intervention to prevent one of the outcomes listed in this definition.

#### 11.3 PROCEDURES FOR REPORTING ADVERSE EVENTS

All AEs and their outcomes must be reported to Ora, the study Sponsor, and the IRB/IEC as required by the IRB/IEC, federal, state, or local regulations and governing health authorities and recorded on the appropriate eCRF.

#### 11.3.1 Reporting a Suspected Unexpected Adverse Reaction

All AEs that are 'suspected' and 'unexpected' are to be reported to Ora, the study Sponsor and the IRB/IEC as required by the IRB/IEC, federal, state, or local regulations and governing health authorities.

#### 11.3.2 Reporting a Serious Adverse Event

To ensure subject safety, all SAEs, regardless of relationship to the IP, must be immediately reported. All information relevant to the SAE must be recorded on the appropriate eCRF. The Investigator is obligated to pursue and obtain information requested by Ora and/or the sponsor in addition to that information reported on the eCRF. All subjects experiencing a SAE must be followed up and the outcome reported. Additionally, in this study there are no expected SAEs and all SAEs will be considered suspected unexpected serious adverse reactions (SUSARs).

In the event of a SAE, the Investigator must notify Ora and the Sponsor Medical Monitor immediately; obtain and maintain in his/her files all pertinent medical records, information, and medical judgments from colleagues who assisted in the treatment and follow-up of the subject; provide Ora and the Sponsor's Medical Monitor with a complete case history, which includes a statement as to the relationship to the IP; and inform the IRB of the SAE within their guidelines for reporting SAEs.

Contact information for reporting SAEs:

Confidential Page 47 of 81

#### 11.4 PROCEDURES FOR UNMASKING (IF APPLICABLE)

When medically necessary, the Investigator may need to determine what treatment has been assigned to a subject. When possible (ie, in non-emergent situations), Ora and/or the study sponsor should be notified before unmasking IP.

# 11.5 TYPE AND DURATION OF THE FOLLOW-UP OF SUBJECTS AFTER ADVERSE EVENTS

The Investigator will follow unresolved adverse events to resolution until the patient is lost to follow-up or until the adverse event is otherwise explained. Resolution means the patient has returned to baseline state of health or the Investigator does not expect any further improvement or worsening of the adverse event. If the patient is lost to follow-up, the Investigator should make 3 reasonable attempts to contact the patient via telephone, post, or certified mail. All follow-up will be documented in the subject's source document. Non-serious adverse events identified on the last scheduled contact must be recorded on the AE eCRF with the status noted.

If the Investigator becomes aware of any new information regarding a Serious Adverse Event (i.e., resolution, change in condition, or new treatment), a new Serious Adverse Event/Unanticipated Report Form must be completed and faxed to Ora Inc. within 24 hours. The original SAE form is not to be altered. The report should describe whether the event has resolved or continues and how the event was treated.

#### 12 STATISTICAL HYPOTHESES AND METHODS OF ANALYSES

#### 12.1 STATISTICAL ANALYSIS PLAN

[figure not shown]
The material described in this section is the basis for the Statistical Analysis Plan (SAP) for this study. The SAP will detail all analyses that will be performed and may include additional exploratory analyses not explicitly mentioned in the following sections. The SAP may be revised during the study to accommodate Clinical Trial Protocol

Confidential Page 48 of 81

Amendments and to make changes to adapt to unexpected issues in study execution and/or data that affect the planned analyses. Any deviations from the final SAP will be provided in the final clinical study report.

[figure not shown]
#### 12.2 STUDY POPULATIONS

12.2.1 Intent-to-Treat Population

Confidential Page 49 of 81

# 12.5 EFFICACY ANALYSES

# 12.7 INTERIM ANALYSIS

No interim analyses are planned.

Confidential Page 50 of 81

# 13 COMPLIANCE WITH GOOD CLINICAL PRACTICES, ETHICAL CONSIDERATIONS, AND ADMINISTRATIVE ISSUES

This study will be conducted in compliance with the protocol, current Good Clinical Practices (GCPs), including the International Conference on Harmonization (ICH) Guidelines, and in general, consistent with the Declaration of Helsinki. In addition, all applicable local, state, and federal requirements relevant to the use of investigational products in the countries involved will be adhered to.

#### 13.1 PROTECTION OF HUMAN SUBJECTS

#### 13.1.1 Subject Informed Consent

Informed consent must take place before any study specific procedures are initiated. Signed and dated written informed consent must be obtained from each subject prior to enrollment into the study.

All informed consent forms must be approved for use by the sponsor and receive approval/favorable opinion from an IRB/IEC prior to their use. If the consent form requires revision (eg, due to a protocol amendment or significant new safety information), it is the Investigator's responsibility to ensure that the amended informed consent is reviewed and approved by Ora prior to submission to the governing IRB/IEC and that it is read, signed and dated by all subjects subsequently enrolled in the study as well as those currently enrolled in the study.

Informed consent may be obtained prior to Visit 1 if the subject wishes to review and discuss the Informed Consent with the Investigator or wishes to get a skin test prior to Visit 1. However, informed consent must be obtained prior to Visit 1 if any of the following criteria are determined during the telephone screening process:

- Proper washout of certain medications is necessary
- Sufficient time of discontinuation of contact lens wear is necessary
- Post-operative period

Medical/medication history, demographics, skin test and inclusion/exclusion review may be performed at the time of informed consent signing prior to Visit 1 (Screening Visit), but must be confirmed at Visit 1 (with the exception of demographics and skin test).

If informed consent is taken under special circumstances (oral informed consent), then the procedures to be followed must be determined by Ora and/or study sponsor and provided in writing by Ora and/or study sponsor prior to the consent process.

Prior to the completion of the Screening Visit, if it is determined a subject did not in fact meet certain washout criteria, the subject may be brought back at a later date to reattempt the screening process.

Confidential Page 51 of 81

Subjects can be re-screened a maximum of three times.

#### 13.1.2 Institutional Review Board (IRB) Approval

This study is to be conducted in accordance with Institutional Review Board regulations (U.S. 21 CFR Part 56.103). The Investigator must obtain appropriate IRB approval before initiating the study and re-approval at least annually.

Only an IRB/ERC approved version of the ICF will be used.

#### 13.2 ETHICAL CONDUCT OF THE STUDY

This study will be conducted in accordance with the ethical principles that originated with the Declaration of Helsinki.

#### 13.3 SUBJECT CONFIDENTIALITY

All personal study subject data collected and processed for the purposes of this study should be maintained by the Investigator and his/her staff with adequate precautions as to ensure that the confidentiality of the data in accordance with local, state, and federal laws and regulations.

Monitors, auditors and other authorized representatives of Ora, the sponsor, the IRB/IEC approving this study, the Food and Drug Administration, the Department of Health and Human Services, other domestic government agencies, and other foreign regulatory agencies will be granted direct access to the study subject's original medical and study records for verification of the data and/or clinical trial procedures. Access to this information will be permitted to the aforementioned individuals to the extent permitted by law.

A report of the results of this study may be published or sent to the appropriate health authorities in any country in which the investigational product may ultimately be marketed, but the subject's identity will not be disclosed in these documents.

#### 13.4 DOCUMENTATION

Source documents may include a subject's medical records, hospital charts, clinic charts, the Investigator's study subject files, as well as the results of diagnostic tests such as X-rays, laboratory tests, and electrocardiograms. The Investigator's copy of the eCRFs serves as the Investigator's record of a subject's study-related data.

#### 13.4.1 Retention of Documentation

All study related correspondence, subject records, ICFs, record of the distribution and use of all IPs and copies of eCRFs should be maintained on file for at least 2 years after the last approval of a marketing application in an ICH region and until there are no pending or contemplated marketing applications in an ICH region; or until at least 2 years have

Confidential Page 52 of 81

elapsed since the formal discontinuation of clinical development of the IP. These documents will be retained for a longer period if required by the applicable regulatory requirements or by an agreement with the sponsor. It is the responsibility of the sponsor to inform the Investigator/institution as to when these documents no longer need to be retained.

If the responsible Investigator retires, relocates, or for other reasons withdraws from the responsibility of keeping study records, custody must be transferred to a person who will accept the responsibility. The sponsor must be notified in writing of the name and address of the new custodian.

# 13.5 LABELING, PACKAGING, STORAGE, ACCOUNTABILITY, AND RETURN OR DISPOSAL OF INVESTIGATIONAL PRODUCT

#### 13.5.1 Labeling/Packaging

ST266 and placebo will be provided to the clinical site(s) in
One ready-to-use ampoule i intended per treatment per subject. Once an ampoule is opened, it is not to be re-used.
13.5.2 Storage of Investigational Product
The IP must be stored in a secure area accessible only to the Investigator and his/her designees. The IP is to be stored refrigerated administered only to subjects entered into the clinical study, in accordance with the conditions specified in this protocol.

#### 13.5.3 Accountability of Investigational Product

The IP is to only be prescribed by the principal investigator or his/her named sub investigator(s), and is to only be used in accordance with this protocol. The IP must only be distributed to subjects properly qualified under this protocol to receive IP.

The Investigator must keep an accurate accounting of the IP received from the supplier. This includes the amount of IP dispensed to subjects, amount of IP returned to the Investigator by the subjects, and the amount returned or disposed upon the completion of the study. A detailed inventory must be completed for the IP.

#### 13.5.4 Return or Disposal of Investigational Product

All IP will be returned to the sponsor or their designee or destroyed at the study site. The return or disposal of IP will be specified in writing.

Confidential Page 53 of 81

# 13.6 RECORDING OF DATA ON SOURCE DOCUMENTS AND CASE REPORTS FORMS (CRFS)

The Investigator is responsible for ensuring that study data is completely and accurately recorded on each subject's eCRF, source document, and all study-related material. All study data should also be attributable, legible, contemporaneous, and original. Recorded datum should only be corrected in a manner that does not obliterate, destroy, or render illegible the previous entry (eg, by drawing a single line through the incorrect entry and writing the revision next to the corrected data). An individual who has corrected a data entry should make clear who made the correction and when, by adding to the correction his/her initials as well as the date of the correction.

#### 13.7 HANDLING OF BIOLOGICAL SPECIMENS

Not Applicable.

#### 13.8 PUBLICATIONS

Publication will be in accordance with the terms of Section 6 – Publicity and Publication set forth in the Master Service Agreement, (the "AGREEMENT) dated October 07, 2016.

Confidential Page 54 of 81

# **APPENDIX 1**

# SCHEDULE OF VISITS AND MEASUREMENTS

Confidential Page 56 of 81

Noveome Biotherapeutics, Inc. Amendment V3.0/13Jan2017

[figure not shown]

Confidential Page 57 of 81

[figure not shown]
### **APPENDIX 2**

# EXAMINATION PROCEDURES, TESTS, EQUIPMENT, AND TECHNIQUES

[figure not shown]
Visual Acuity Procedures (ETDRS Chart)

[figure not shown]
Confidential Page 58 of 81

Confidential Page 59 of 81

Confidential Page 60 of 81

Ora proprietary scales - Not for distribution without permission

Confidential Page 61 of 81

[figure not shown]
#### Allergen Challenge Scales

Ora proprietary scales - Not for distribution without permission

Confidential Page 62 of 81

# Nasal Allergic Symptoms

Ora Proprietary Scales - Not for distribution without permission

Confidential Page 63 of 81

# Investigator-Evaluated Signs (Ocular)

[figure not shown]
Ora Proprietary Scales - Nor for distribution without permission

Confidential Page 64 of 81

# Subject-Reported Drop Comfort Scale

Ora CalibraTM Drop Comfort Questionnaire

Confidential Page 65 of 81

#### APPENDIX 3

### SAMPLE DOSING INSTRUCTIONS AND DIARY PAGE

Sample Dosing Diary Instructions: Visits 3 to 4a Dosing Diary

[figure not shown]
#### DOSING INSTRUCTIONS

	•	
_		
_		

Confidential Page 66 of 81

# Sample Dosing Diary Instructions: Visits 3 to 4a Dosing Diary

#### **GENERAL INSTRUCTIONS**

Confidential Page 67 of 81

# Sample Dosing Diary Instructions: Visits 4b to 5a Dosing Diary

[figure not shown]
# DOSING INSTRUCTIONS

•			
	_		

Confidential Page 68 of 81

# Sample Dosing Diary Instructions: Visits 4b to 5a Dosing Diary

#### **GENERAL INSTRUCTIONS**

Confidential Page 69 of 81

# Sample Daily Assessments Instructions: Visits 4b to 5a Daily Assessments Diary

# DIARY INSTRUCTIONS

_		

Confidential Page 70 of 81

# Sample Dosing Diary Instructions: Visits 5b to 6 Dosing Diary

[figure not shown]
# DOSING INSTRUCTIONS

•	

Confidential Page 71 of 81

# Sample Dosing Diary Instructions: Visits 5b to 6 Dosing Diary

#### **GENERAL INSTRUCTIONS**

Confidential Page 72 of 81

# Sample Daily Assessments Instructions: Visits 5b to 6 Daily Assessments Diary

# DIARY INSTRUCTIONS

Confidential Page 73 of 81

# **APPENDIX 4**

[figure not shown]
# PACKAGE INSERT/ INVESTIGATIONAL PRODUCT COMPOSITION/ DESIGN (IF APPLICABLE)

Confidential Page 74 of 81

# **APPENDIX 5**

# PROTOCOL AMENDMENT SUMMARY

Confidential Page 75 of 81

Noveome Biotherapeutics, Inc. Amendment V3.0/13Jan2017

Confidential Page 76 of 81

Noveome Biotherapeutics, Inc. Amendment V3.0/13Jan2017

Confidential Page 77 of 81

Noveome Biotherapeutics, Inc. Amendment V3.0/13Jan2017

Confidential Page 78 of 81

#### APPENDIX 6

This SAP is being written with due consideration of the recommendations outlined in the most recent International Conference on Harmonization (ICH) E9 Guideline entitled Guidance for Industry: Statistical Principles for Clinical Trials and the most recent ICH E3 Guideline, entitled Guidance for Industry: Structure and Content of Clinical Study Reports (CSR).

This SAP describes the data that will be analyzed and the subject characteristics, efficacy, and safety assessments that will be evaluated. This SAP provides details of the specific statistical methods that will be used. The statistical analysis methods presented in this document will supersede the statistical analysis methods described in the clinical protocol. If additional analyses are required to supplement the planned analyses described in this SAP they may be completed and will be identified in the CSR.

2. Study Objectives

The primary objective of this study is to evaluate the efficacy of ST266 ophthalmic drops compared to placebo for the treatment of the signs and symptoms of allergic conjunctivitis.

3. Study Variables

3.1 Primary Variables

The primary efficacy variables are the following:

- Ocular itching evaluated by the subject at all time points [REDACTED] at Visits 5b and 6.
- Conjunctival redness evaluated by the investigator at all time points [REDACTED] [REDACTED] at Visits 5b and 6.

3.2 Secondary Variables

The following secondary efficacy assessments will occur pre-CAC and at [REDACTED]

[REDACTED] post-CAC [REDACTED] at Visits 5b and 6:

- Ciliary redness evaluated by the investigator
- Episcleral redness evaluated by the investigator
- Chemosis evaluated by the investigator
- Eyelid swelling evaluated by the subject
- Tearing evaluated by the subject
- Rhinorrhea, nasal pruritus, ear or palate pruritus, and nasal congestion evaluated by the subject
- A composite score of presence or absence of at least one nasal symptom evaluated by the subject

All assessments will be evaluated at pre-CAC and [REDACTED] minutes post-CAC at Visits 4a, 4b, and 5a.

3.3 Exploratory Variables

The exploratory efficacy variables include the following:

- Conjunctival Inflammation Score (CIS) evaluated by a masked clinician using confocal microscopy post-CAC [REDACTED] Visit 6 (subset of [REDACTED] subjects at one center).
 - Diary assessments for all subjects. Assessments of ocular itching, ocular redness, and eyelid swelling will occur prior to bedtime and upon awakening from Visit 4b to Visit 6 ([REDACTED])

3.4 Safety Variables

The safety variables include the following:

- Adverse Events
 - Visual Acuity at Distance Utilizing an ETDRS chart
 - Slit-lamp Biomicroscopy
 - Intraocular Pressure
 - Dilated Fundoscopy

3.5 Statistical Hypotheses

The null and alternative hypotheses, based on the primary variables, are as follows:

[figure not shown]
All hypothesis testing will be two-sided with a type I error rate (α) of [REDACTED]. The above hypothesis tests will be applied to Visit 5b and Visit 6 separately. No multiplicity corrections will be employed in this Phase 2 exploratory efficacy study. Specifics of the statistical tests are provided in Section 14.

4. Study Design and Procedures

4.1 General Study Design

[figure not shown]
Study visits will be referred to in all tables and listings as the expected study day corresponding to the visit to enable reviewers to understand the assessment timing without referring to the protocol visit

schedule. The following table shows the scheduled study visits, their planned study day, and the acceptable visit window for each study visit:

4.2 Schedule of Visits and Assessments

The schedule of visits and assessments is provided below.

5. Study Treatments

The investigational treatment for this study is ST266 ophthalmic drops. The control is placebo (0.9% Sodium Chloride) ophthalmic drops.

5.1 Method of Assigning Subjects to Treatment Groups

On Day -2 (Visit 1), subjects who provide verbal and written informed consent will be assigned a unique 4-digit subject ID, which consists of the 1-digit site number plus a unique 3-digit screening number (beginning with 001 within each site). The 3-digit screening numbers must be assigned in ascending consecutive order.

Once a subject meets all qualification criteria, they will be randomly assigned to masked treatment using a [REDACTED] assignment ratio.

Subjects will be randomized on Visit 3 (Day 1) by assignment of the next 4-digit randomization number available at each investigative site. The randomization number will be stratified by the average post-CAC itching scores [REDACTED] at baseline [REDACTED] [REDACTED] to ensure balance within treatment groups for the primary endpoint of ocular itching. No randomization numbers will be skipped or omitted.

A computer-generated randomization schedule will be produced prior to study enrollment by an unmasked statistician who is not otherwise involved in the study. Each randomization number will correspond to a treatment group assignment and subject supplies will be labeled according to the randomization list and dispensed at each site.

The 4-digit subject ID will be used to identify subjects in all datasets and listings for this study.

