## Measures Taken to Reduce Bias:

Randomization will be used to avoid bias in the assignment of subjects to investigational product, to increase the likelihood that known and unknown subject attributes (e.g. demographics and baseline characteristics) are evenly balanced across treatment groups, and to enhance the validity of statistical comparisons across treatment groups. In addition, randomization will be stratified by

Finally, masked treatment will be

used to reduce potential of bias during data collection and evaluation of clinical endpoints.

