## 8.1.3 Criteria for Effectiveness

This clinical study is designed to evaluate the efficacy of ST266 ophthalmic drops compared to placebo for the treatment of the signs and symptoms of allergic conjunctivitis.

To demonstrate efficacy for ocular itching and conjunctival redness, ST266 ophthalmic drops need to show clinical superiority over placebo by at least 0.5 units of a 5 point scale for all three (3) post-CAC time points:

post-CAC for conjunctival redness, and at least 1 unit for the majority (2:3) of these post-CAC time points for each primary endpoint.

If ocular itching meets statistical significance and the criteria for clinical efficacy as defined above, then the study will be considered a success for ocular itching. In addition, if conjunctival redness then also meets statistical significance and the criteria above for clinical success, then the study will be considered a success for both ocular itching and conjunctival redness.

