14.1 Primary Analysis

The primary efficacy endpoints are ocular itching assessed at all time points [REDACTED] [REDACTED] and conjunctival redness assessed at all time points [REDACTED] [REDACTED] at Visit 5b and Visit 6. [REDACTED] [REDACTED]. Ocular itching and conjunctival redness will each be analyzed using an [REDACTED] [REDACTED] [REDACTED] Least squares means (LS Means) for each treatment, LS Means treatment differences, and 95% confidence intervals (CIs) for the LS Means treatment differences will be provided.

Multiple imputation employing the MCMC method will be performed for the primary analysis of the primary endpoints using the SAS procedure PROC MI by applying the following SAS code:

[REDACTED]

where

[REDACTED]

After obtaining twenty complete data sets, the following SAS code will be employed to run the model on each data set:

[REDACTED]

where

[REDACTED]

Then, the following SAS code will be used to analyze the combined data:

[REDACTED]

The primary efficacy analyses will be conducted on the ITT population using MCMC multiple imputation methodology for missing data, as described in Section 9.2 and above. Adjustments for multiplicity will not be employed in this exploratory Phase 2 study.

Sensitivity or supportive analyses will be performed on the ITT population, using LOCF and observed data only, as well as on the PP population with observed data only.

Two-sample *t*-tests will be used as additional sensitivity analyses at each post-CAC® time point, as well as non-parametric Wilcoxon rank sum tests for comparing ST266 ophthalmic drops and placebo. Mean treatment differences, 95% CIs for each of the means, and 95% CIs for the mean differences will be presented.

In addition, ANCOVA models will be run separately at Visit 5b and Visit 6 as secondary analyses, with treatment, time point, and time appropriate baseline as covariates for adjustment (accounting for repeated measurements). LS Means for each treatment, the LS Means treatment difference between ST266 ophthalmic drops and placebo, and the corresponding 95% CIs will be calculated from these ANCOVA models. SAS pseudo-code for the ANCOVA model accounting for repeated measures at each Visit follows:

[REDACTED]

An unstructured variance-covariance matrix will be used for the above repeated measures model. If the model does not converge using the unstructured matrix, the first order autoregressive structure and the compound symmetry structure will be employed, in that order.

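### The repeated-measures model for conjunctival redness (SAP 14.1) does not list the baseline-itching stratum used to randomise; adding it would slightly narrow the interval if baseline itching predicts redness

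*SAP*

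**What the plan says.** **Randomisation.** SAP 5.1: "The randomization number will be stratified by the average post-CAC itching scores" at baseline, with the cut-off blacked out. The stated purpose is "to ensure balance within treatment groups for the primary endpoint of ocular itching". On sites, the same section says "Subjects will be randomized on Visit 3 (Day 1) by assignment of the next 4-digit randomization number available at each investigative site", and that "subject supplies will be labeled according to the randomization list and dispensed at each site". It does not say that the list is blocked within site. The matching sentence in the protocol synopsis begins "In addition, randomization will be stratified by" and is then blacked out.

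**Analysis.** SAP 14.1 runs a repeated-measures ANCOVA separately at Visits 5b and 6, as a secondary analysis, "with treatment, time point, and time appropriate baseline as covariates for adjustment". Neither the itching stratum nor site is named. The pseudo-code for this model is redacted, and so are the form and covariates of the primary model.

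**Baseline.** SAP 9.3 defines baseline parameter by parameter, generally at Visit 3. The redness model therefore adjusts for baseline redness.

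**Endpoint.** SAP 3.1 names as a primary variable "Conjunctival redness evaluated by the investigator at all time points" at Visits 5b and 6. SAP 14.2 has the quantitative secondary endpoints analysed much as the primary ones, followed by redacted lines.

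**The concern.** When randomisation is restricted by a factor, the usual practice is to put that factor in the model, so that the standard error reflects the balance the design has bought. The itching model does this through its own baseline. The redness model, as listed, does not.

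If subjects who itch more at baseline also redden more at follow-up, beyond what their baseline redness predicts, that variation stays in the residual. The reported redness interval is then slightly wider than it need be. A stable grading difference between the two centres would act in the same way, because redness is graded by the investigator. At stake is a little width in the intervals of a secondary model.

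**Working it through.** The documents give no standard deviation, power or precision figure, so there is no plan figure to reproduce.

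**Inputs from the documents.** About 70 subjects at two centres (Protocol 7.1); 95% intervals (SAP 14.1); three post-CAC time points (Protocol 8.1.3, "for all three (3) post-CAC time points").

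**Assumed, because redacted or not given.** 1:1 allocation; two itching strata split at the mean; permuted blocks of 4; two equal sites; baseline-to-follow-up correlation r of 0.3 to 0.7; partial correlation p of baseline itching with follow-up redness of 0 to 0.3.

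**Step 1: expected size.** If itching is roughly normal, a split at the mean keeps 2/π = 0.637 of its squared correlation. If itching is also unrelated to baseline redness, the stratum explains R² = 0.637p² of the residual variance, and the width ratio is √(1 − R²):

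- p = 0.1: R² = 0.0064, ratio 0.9968, 0.3% narrower
- p = 0.2: R² = 0.0255, ratio 0.9872, 1.3% narrower
- p = 0.3: R² = 0.0573, ratio 0.9709, 2.9% narrower

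The extra term costs a little under 0.1% in every case.

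**Step 2: simulation.** Change in mean 95% interval width against treatment plus baseline redness, 4,000 trials per cell:

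| Added term | p = 0 | p = 0.1 | p = 0.2 | p = 0.3 |
|---|---|---|---|---|
| Stratum, r = 0.3 | +0.07% | −0.27% | −1.21% | −2.89% |
| Stratum, r = 0.5 | +0.08% | −0.23% | −1.19% | −2.90% |
| Stratum, r = 0.7 | +0.09% | −0.24% | −1.24% | −2.93% |
| Continuous baseline itching, r = 0.5 | +0.31% | −0.17% | −1.74% | −4.36% |

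**Step 3: repeated-measures form.** This check used three time points, within-visit correlation 0.7, time-specific baselines, an unstructured covariance, r = 0.5 and 800 trials per cell. The stratum term gave +0.08%, −0.33%, −1.56% and −3.39% for p = 0, 0.1, 0.2 and 0.3.

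**Step 4: width against true spread.** With the stratum balanced across arms, its effect largely cancels from the treatment difference whether or not it is modelled. At p = 0.2 and 0.3 (r = 0.5, 3,000 trials) the interval narrows by 1.2% and 2.9%, but the empirical standard deviation of the treatment estimate falls by only 0.1% and 0.2%. The term mainly brings the reported standard error down to the spread that the design already delivers.

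**Step 5: test size without the added terms.** With blocking by site and stratum, and p of 0.2-0.3 or a site shift of 0.5-1 SD, the rejection rate under no effect was 0.035-0.052 against a nominal 0.05 (Monte Carlo error about 0.007). The test is at most slightly conservative.

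**Step 6: scale in score units.** With an assumed residual SD of 0.8 and 35 per group, SE = 0.8 × √(2/35) = 0.191 and the 95% half-width is about 1.996 × 0.191 = 0.38 units. A 2.9% reduction is 0.38 × 0.029 = 0.011 units, beside a smallest success threshold of 0.5 units (Protocol 8.1.3).

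**Step 7: itching, for contrast.** Adding the stratum to the itching model, which already has baseline itching, widens its interval by 0.51-0.57%.

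**Step 8: site, for redness.** A grading shift is taken as equal at baseline and follow-up, with p = 0. Ranges are over r = 0.3 to 0.7:

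| Randomisation list | No shift | 0.5 SD | 1 SD |
|---|---|---|---|
| Blocked within site | +0.05 to +0.07% | −0.43 to −1.43% | −1.56 to −4.87% |
| Not blocked within site | +0.76 to +0.82% | −0.83 to +0.22% | −0.94 to −4.41% |

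**The case against.** The strongest case against is that nothing decisive hangs on this model. It is a secondary analysis in an exploratory trial, and nothing shows that the success criteria in Protocol 8.1.3 are judged on it. That stands, and it keeps the point small.

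Second, absence cannot be proved: the pseudo-code is redacted and the prose list may be a summary. This stands as a limit. If the hidden code already holds the stratum, the prose should be brought into line with it.

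Third, the stratification was aimed at itching, and the itching model handles it. That is true, but the factor still restricts the allocation of every subject whose redness is analysed.

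Fourth, the narrowing is mostly not new information. Step 4 confirms this, so a reader should not convert it into subjects saved.

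Fifth, the gain is conditional. If baseline itching does not predict redness, the interval is about 0.1% wider. This also stands.

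A reader might go further and infer any of the following, which the documents do not support:

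- **That the primary analysis ignores the stratification.** Its covariates are redacted, so nothing can be said.
- **That the omission biases the redness result or inflates false positives.** Leaving out a balanced prognostic factor does neither; Step 5 shows a test that is at most conservative.
- **That site is a stratification factor.** SAP 5.1 shows numbers and supplies issued by site; blocking within site is at most implied.
- **That the imputation model in SAP 9.2 needs the same term.** SAP 14.1 ties imputation to the redacted primary analysis, and no text says that it feeds this model.
- **That site belongs in the itching model.** Only a small cost was calculated there (0.06-0.08% wider if blocked, with no site effect assumed), and no benefit was shown.

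**Conclusion.** The point holds as an optional refinement. The listed terms of the repeated-measures model for conjunctival redness leave out the factor on which randomisation was stratified. Adding the stratum narrows the redness interval by about 0.2-0.3%, 1.2% or 2.9% at partial correlations of 0.1, 0.2 and 0.3, and widens it by about 0.1% if there is no link. The effect is chiefly a standard error that no longer slightly overstates the estimate's spread.

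The direction is secure. The size depends on assumed allocation, strata, block size and correlations, none of which the documents give. Extending the point to other non-itching quantitative endpoints is conditional on their being analysed by the same model, which the redactions in SAP 14.2 leave open.

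**What to change.** In SAP 14.1, add the baseline-itching randomisation stratum as a covariate in the repeated-measures model for conjunctival redness, and in the models for other non-itching quantitative endpoints where the same model is used. Leave the itching model as it is.

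Optionally, add site as a fixed effect for the investigator-graded signs (conjunctival, ciliary and episcleral redness, and chemosis) if the randomisation list was blocked within site. State in SAP 5.1 whether it was.

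Continuous baseline itching could replace the stratum. It gains more at partial correlations of 0.2 and 0.3, but costs about 0.3% in width if there is no link.

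The change is SAP wording only, needs no new data, and should be made before treatment codes are released so that the covariates are not chosen after seeing results. If the added terms explain nothing, the redness interval is about 0.1% wider with the stratum alone, and 0.1-0.2% wider with stratum and site when the list is blocked within site. With continuous itching and site, the cost is about 0.4% when blocked.
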